11.1 Sample Size Determination

About 50 subjects (n=25 per treatment arm) are planned for randomization in the study.

Sample size has been determined to reflect the exploratory nature of this study.

11.2 Study Analysis Populations

The following analysis populations will be used in this study:

- Modified-intent-to-treat (MITT) population: All randomized subjects who receive at least 1 dose of study drug starting from baseline (Day 1) visit, have at least one pre-treatment Hb measurement, and at least one post-treatment Hb measurement. Subjects in the MITT population will be analyzed based on their randomized treatment assignment.
- Per-protocol population: All randomized subjects who receive at least 1 dose of study drug starting from baseline (Day 1) visit, have at least one pre-treatment Hb measurement, have at least one post-treatment Hb measurement, have epoetin alfa dose recorded during Week 18 to 20, and did not receive any rescue therapy from Weeks 12 to 20. Subjects in the per-protocol population will be analyzed based on their randomized treatment assignment.
- Safety population will include subjects who received at least 1 dose of study drug. Subjects in the safety population will be analyzed based on the study drug treatment that they received.

Efficacy analyses will utilize the MITT and per-protocol populations. Safety analyses will utilize the safety population.

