7.6.2 Individual Subject Study Drug Discontinuation or Individual Subject Discontinuation

The investigator must document the primary reason for temporary or permanent study drug discontinuation on the case report form (CRF). For subjects who discontinue study drug, the investigator should resume treatment based on standard of care and clinical judgment.

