8.3.4 Dosing Regimen for the Epoetin Alfa Treatment Arm

For subjects who are randomized to the epoetin alfa treatment arm, the initial dosing regimen in the study (starting from baseline [Day 1] visit) will be the same dose that they were receiving during the screening period.

Epoetin alfa dose will be administered and titrated as clinically indicated based on an individual subject's central lab Hb value and the approved label for adult patients with CKD on dialysis.

8.3.5 Dosing Regimen for the Vadadustat Treatment Arm and Guidelines for Vadadustat Dose Adjustment

Subjects assigned to the vadadustat arm will discontinue epoetin alfa and take vadadustat once daily for 20 weeks.

The following dosing regimen are for subjects who are randomized to the vadadustat treatment arm:

- Vadadustat dosing (Day 1 to Week 20)
 - Starting dose of vadadustat: once daily) starting at baseline/Day 1. The first dose of vadadustat will be administered at the investigative site after other baseline procedures have been completed. Thereafter, vadadustat will be taken once daily in the dialysis centers or on an outpatient basis.
 - The vadadustat dose can be up-titrated every 4 weeks or down-titrated more frequently based on the target Hb range of 10.0-11.0 g/dL.

 - Dosing instructions: Subjects should be instructed to swallow intact tablet(s) of vadadustat with water or another beverage. Subjects may take vadadustat with or without food. The full dose should be taken at approximately the same time each day. The subject should be instructed to take any oral iron supplements (including multivitamins containing iron), iron containing phosphate binders, or any medication containing iron at least 2 hours before or 2 hours after taking the vadadustat dose.
 - After the end of vadadustat treatment at Week 20 (or following early discontinuation of vadadustat), subjects will resume dosing with epoetin alfa (or another ESA), based on the approved label for adult patients with CKD on dialysis.

Guidelines for Vadadustat Dose Adjustments

Vadadustat dose adjustments will be guided by an IWR system based on the Hb value and programmed Dose Adjustment Algorithms (as presented below).

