8.3.8 Continuation of Study Drug Treatment

Subjects in the vadadustat treatment arm will not receive vadadustat past the treatment period of approximately 20 weeks. Subjects in the vadadustat treatment arm who complete Week 20, or discontinue early, will resume dosing with epoetin alfa (or another ESA) at Week 20 after all EOT procedures are completed.

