8.3.10 Rescue Therapy Guidelines

Hemoglobin levels will be monitored throughout the study at scheduled visits and can be measured more frequently based on investigator's clinical judgment.

Rescue therapy with RBC transfusion or epoetin alfa are allowed, but not required during the treatment period. The following rescue therapy guidelines are provided to ensure the safety of study subjects and to standardize the use of rescue in the study. In cases of extenuating clinical circumstances, the investigator may elect to dose outside the rescue therapy guidelines to maintain the Hb within the target range. In such cases, the clinical circumstances should be documented in the subject's record.

- RBC transfusion: Investigators should use their investigative site's transfusion guidelines when determining whether to transfuse a study subject. In general, in the event of an acute or severe loss of blood, RBC transfusion should be administered as clinically indicated. In less severe instances but where there may be worsening of anemia or moderate to severe symptoms of anemia, RBC transfusions are permitted based on the investigator's clinical judgment. Study drug (vadadustat or epoetin alfa) may be continued during the RBC transfusion period.
 - Epoetin alfa rescue therapy: Starting at Week 6, subjects in both treatment arms will be allowed (although not required) to have their Hb rescued with epoetin alfa. When possible, a subject on vadadustat should be on maximum dose of vadadustat for 2 weeks prior to epoetin alfa rescue. Epoetin alfa rescue therapy should be administered based on the approved US product label for adult patients with CKD on dialysis.
 - To qualify for epoetin alfa rescue therapy, each of the following conditions must be fulfilled.

NOTE: Epoetin alfa rescue therapy should be stopped when Hb is ≥ 9.0 g/dL.

- The subject has experienced a clinically significant worsening of their anemia or symptoms of anemia (eg, fatigue, weakness, shortness of breath, chest pain, confusion, or dizziness) compared to baseline
- The subject's Hb is confirmed to be <9.0 g/dL
- The Hb level decreased >0.5 g/dL from baseline
- Reducing the risk of alloimmunization or transfusion-related risks or both is a goal
- For the epoetin alfa treatment arm:

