 - In addition to meeting the rescue criteria noted above, dosing and administration of epoetin alfa rescue therapy should be based on the approved label for adult patients with CKD on dialysis.

- For the vadadustat treatment arm:
 - Epoetin alfa rescue may not be considered until the next study visit if a subject's current vadadustat dose can be increased (ie, if the subject's last vadadustat dose increase was at least 4 weeks earlier and the subject is currently receiving a vadadustat dose of 600 mg/day or less, then vadadustat dose can be increased by 1 tablet to maintain Hb within the target range of 10.0-11.0 g/dL).

NOTE: vadadustat must be temporarily interrupted during epoetin alfa rescue therapy. After epoetin alfa rescue therapy is completed, vadadustat should be resumed and adjusted per the dose adjustment guidelines (Section 8.3.5).

A minimum interval must be observed prior to restarting vadadustat after the last dose of rescue medication, and treatment may be resumed 2 days after last dose of epoetin alfa rescue.

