8.4.2 Erythropoiesis-Stimulating Agents

Subjects are prohibited from taking non-protocol ESAs starting from the screening period and through Week 20, unless the subject permanently discontinues study treatment.

Epoetin alfa rescue therapy is allowed as presented in Section 8.3.10.

8.4.3 RBC Transfusion, Epoetin Alfa Rescue Therapy, Iron Supplementation, and Therapeutic Phlebotomy

Use of epoetin alfa rescue therapy, iron supplementation, and therapeutic phlebotomy within 30 days prior to Day 1 will be recorded.

Receipt of RBC transfusion, epoetin alfa rescue therapy, iron supplementation, and therapeutic phlebotomy during the study will be recorded.

NOTE: RBC transfusion within 4 weeks prior to or during screening is a study exclusion criterion.

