9.4.4 Week 20 Visit (End-of-Treatment)

On the day of the Week 20 visit, the vadadustat dose will be taken at the investigative site after a blood sample for PK analysis has been collected.

At the Week 20 visit, the following activities/procedures will be performed:

- Review acceptable methods of contraception
- Dry weight and dialysis treatment review
- Dialysis adequacy
- Vital signs
- AE review
- Concomitant medication review
- Laboratory procedures (if blood samples are collected on a day of dialysis, blood draws should be done prior to dialysis, if applicable):
 - CBC with differential
 - o Reticulocyte count
 - C-reactive protein
 - Serum chemistry
 - Liver function tests
 - \circ Iron indices
 - Lipid panel
 - 2 samples for PK analyses (vadadustat treatment arm only; the first sample will be collected prior to vadadustat administration and the second sample will be collected at least 15 minutes post dialysis. If post dialysis collection is not possible, the second sample will be collected at least 3 hours after vadadustat administration. The time of the last dose of vadadustat taken prior to the PK sampling, as well as the timing of the PK sample collection, will be documented)
 - Biomarkers
 - Sample for erythropoietin measurement
 - Sample for exploratory analyses
- Subjects in epoetin alfa treatment arm will continue to receive epoetin alfa

- For subjects in the vadadustat treatment arm only:
 - Vadadustat drug reconciliation
 - Review vadadustat dosing compliance
 - Resume dosing with epoetin alfa (or another ESA): After the end of vadadustat treatment at Week 20 (or following early discontinuation of vadadustat), subjects may resume dosing with epoetin alfa (or another ESA), based on the approved label for adult patients with CKD on dialysis
- Review use of rescue therapy (RBC transfusions and epoetin alfa rescue therapy)
- Review use of iron supplementation
- Review use of therapeutic phlebotomy

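### The per-protocol rule asks for an epoetin alfa dose in Weeks 18-20 in both arms, so vadadustat subjects qualify essentially only through epoetin alfa given off vadadustat

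*Combined protocol and SAP*

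**What the plan says.** Section 11.2 defines one per-protocol population for all randomized subjects, grouped as randomized. Beyond at least one dose of study drug and Hb values before and after treatment, subjects must "have epoetin alfa dose recorded during Week 18 to 20, and did not receive any rescue therapy from Weeks 12 to 20". The section names per-protocol and MITT as the two efficacy populations.

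The treatment rules for the vadadustat arm are elsewhere:

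- Section 8.3.5: "Subjects assigned to the vadadustat arm will discontinue epoetin alfa and take vadadustat once daily for 20 weeks".
- Section 8.4.2: "Subjects are prohibited from taking non-protocol ESAs starting from the screening period and through Week 20, unless the subject permanently discontinues study treatment".
- Section 8.3.10 allows epoetin alfa as rescue: "Starting at Week 6, subjects in both treatment arms will be allowed (although not required) to have their Hb rescued with epoetin alfa". It adds that "vadadustat must be temporarily interrupted during epoetin alfa rescue therapy".
- Section 8.3.8: subjects who complete Week 20 or stop early "will resume dosing with epoetin alfa (or another ESA) at Week 20 after all EOT procedures are completed". Section 9.4.4 words this differently: "subjects may resume dosing with epoetin alfa (or another ESA), based on the approved label". Appendix A marks the resumption in the Week 24 column.

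**The concern.** A per-protocol set should hold subjects who received their assigned treatment broadly as planned. In the epoetin alfa arm, a recorded epoetin alfa dose late in treatment does that job. In the vadadustat arm the same condition asks for a dose of the drug those subjects were told to stop. An adherent, unrescued vadadustat subject fails it unless an epoetin alfa dose after the last vadadustat dose happens to fall in the window. A subject who abandoned vadadustat and returned to epoetin alfa can pass.

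At stake are the per-protocol summaries of the primary endpoint (change in Hb) and the secondary endpoints, with confidence intervals where appropriate (Section 11.6). Section 11.3 also summarizes demographic and pretreatment variables for each analysis population, so those per-protocol tables would carry the same selection.

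**Working it through.** The plan gives no expected size for the per-protocol population, so there is no figure to reproduce. The check is mainly logical.

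**Inputs.** 25 planned subjects per arm (Section 11.1). Two conditions from Section 11.2: *E*, an epoetin alfa dose recorded in Weeks 18-20; *R*, no rescue in Weeks 12-20. Treatment rules from Sections 7.6.2, 8.3.5, 8.3.8, 8.3.10 and 8.4.2.

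**Step 1: vadadustat taken as planned.** Epoetin alfa stops on Day 1 and non-protocol ESAs are barred through Week 20, so the protocol source of epoetin alfa is rescue. Weeks 18-20 lie inside Weeks 12-20, so meeting *E* by rescue breaks *R*. Number qualifying this way: 0 of 25. Even rescue is given with vadadustat interrupted.

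**Step 2: the routes that remain.**

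| Route into the set | What it depends on |
|---|---|
| Early permanent discontinuation, then epoetin alfa | The ESA chosen is epoetin alfa and a dose is recorded in Weeks 18-20 |
| Resumption at Week 20 after end-of-treatment procedures | The ESA is epoetin alfa, the dose counts as within the window, and it is recorded. Sections 8.3.8 and 9.4.4 differ on whether resumption is required, both allow another ESA, and Appendix A places it under Week 24 |
| Epoetin alfa during a temporary interruption | Unsettled. Section 7.6.2 says "For subjects who discontinue study drug, the investigator should resume treatment based on standard of care and clinical judgment" in a paragraph covering temporary and permanent discontinuation, but Section 8.4.2 lifts the ESA bar only for permanent discontinuation |

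Every route is epoetin alfa given after, or away from, vadadustat.

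**Step 3: bounds.** The number entering by these routes lies between 0 and 25. Nothing in the documents narrows that range.

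**Step 4: which early stoppers.** Section 7.6.2.2 gives a 4-week follow-up after permanent discontinuation. A dose at Week 18 or later is then recorded mainly for stops from about 18 - 4 = Week 14. Section 10.1.1 makes an exception for subjects who stop because of a kidney transplant, who stay on the full schedule.

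**Step 5: illustration if a Week 20 dose does not count.** Entry is then essentially limited to early stoppers. The documents give no discontinuation rate, so the rate *d* is assumed. Expected early stoppers = 25*d*, a ceiling on those who qualify. The probability of no early stopper is (1 - *d*)^25. Completers, shut out in this case, number 25(1 - *d*).

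| Assumed *d* | Expected early stoppers | Probability of none | Expected completers shut out |
|---|---|---|---|
| 5% | 1.25 | 0.277 | 23.75 |
| 10% | 2.5 | 0.072 | 22.5 |
| 20% | 5 | 0.004 | 20 |
| 30% | 7.5 | <0.001 | 17.5 |

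The 95% confidence interval half-width for a mean, in SD units, is t(0.975, k-1)/√k: 2.48 for k = 3 and 1.24 for k = 5, against 0.41 for k = 25. In this case the vadadustat per-protocol mean would be both selected and very imprecise.

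**The case against.** The strongest reply is the Week 20 route. A subject who takes vadadustat exactly as planned, with the last dose at the site on the Week 20 visit day, may restart epoetin alfa that same day. All subjects enter the study on epoetin alfa (Section 7.2), and Section 6.2 says the trial runs mostly at one provider's centers, where epoetin alfa has been standard of care. If Week 20 doses count, the vadadustat per-protocol group could be close to the unrescued completers, and a dose given after end-of-treatment procedures cannot alter the Hb already drawn.

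This stands as far as it goes. It rules out saying that no vadadustat subject can enter, and it makes the distortion conditional. It does not rescue the rule. Membership would still turn on which ESA is restarted, on what day, and whether it is recorded, none of which reflects adherence to vadadustat. Two equally adherent completers could be classified differently.

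Two other readings would help: that a recorded dose of zero counts, or that the condition was meant for the epoetin alfa arm alone. The text states neither, and choosing one after seeing Hb results in an open-label study is what prespecification should prevent. The condition may be left over from a design in which vadadustat was added to epoetin alfa. Section 9.3.3 still lists an epoetin alfa dose reduction for the vadadustat arm, and the rapid-rise rule in Section 8.3.5 still refers to subjects not receiving epoetin alfa. That origin is inference and does not change what the rule now does.

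Finally, the study is descriptive, MITT is reported alongside, and Section 11.4 counts inclusion by arm and lists reasons for exclusion. These points limit the harm. The listing shows who was left out but does not correct the rule.

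**Conclusion.** The concern holds. The per-protocol rule selects the vadadustat arm on use of the comparator drug and the epoetin alfa arm on use of its own drug, so the two groups are not defined comparably. The firm figure is 0 of 25 qualifying through treatment received while taking vadadustat as planned. The number entering through epoetin alfa given off vadadustat is unknown, between 0 and 25; either extreme is possible and no value between is supported.

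This rests on reading a recorded epoetin alfa dose as an actual dose and the condition as applying to both arms, which is what the text says. The consequence is limited to per-protocol summaries, so this should be fixed but does not undermine the study's main descriptive results.

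**What to change.** Before the Hb data are analysed, replace the epoetin alfa condition in Section 11.2, for both arms, with: *have dosing information for the randomized study drug (vadadustat or epoetin alfa) recorded during Weeks 18 to 20, including doses withheld or interrupted as the protocol or label directs, and have not permanently discontinued the randomized study drug before Week 18*. The Weeks 12-20 rescue condition can stay.

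Simply deleting the condition is not enough. The current text can admit early stops from about Week 14; deletion would admit stops from Day 1, given one post-treatment Hb value and no rescue in Weeks 12-20. The proposed wording excludes all stops before Week 18.

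The cost is one sentence. Epoetin alfa doses are kept in medical records (Section 8.1), vadadustat compliance comes from accountability logs and questioning (Section 8.3.7), and the reason for any discontinuation is recorded on the CRF (Section 7.6.2). That CRF entry should decide permanent discontinuation in the epoetin alfa arm too, since a subject there may leave study treatment yet continue epoetin alfa as standard of care. One small limit is that scheduled vadadustat reconciliation falls at Weeks 4, 8, 12, 16 and 20, with other visits as applicable. The last scheduled interval is 20 - 16 = 4 weeks, of which only 2 are in the window, so Weeks 18-20 may rest on assigned dose, questioning at Weeks 18 and 20, and that 4-week count.

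Sections 8.3.8 and 9.4.4 and Appendix A should separately be reconciled on ESA resumption. The revised rule does not depend on how that is settled.

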11.3 Analysis of Demographics and Pretreatment Variables

Descriptive statistics will be generated for demographic and pretreatment variables for each analysis population.

Medical history terms will be coded using the Medical Dictionary for Regulatory Activities (MedDRA) and summarized by System Organ Class and Preferred Term for each treatment group based on the safety population.

11.4 Disposition of Subjects

The number and percentage of subjects randomized and included in each analysis population will be summarized by treatment and overall. Reasons for excluding subjects from the analysis populations will be presented in a by-subject listing.

The number of randomized subjects who completed the study, discontinued early from study drug, completed or discontinued from the study, and reasons for discontinuation will be summarized by treatment group and overall.

11.5 Missing Data

It is expected that few subjects will discontinue follow-up for epoetin alfa use. The reasons for any missing data will be summarized by treatment arm. The primary analysis will be based upon observed data without imputation.

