11.6 Efficacy Analyses

This study is exploratory in nature, designed to evaluate the change in Hb from baseline over time during the treatment period. No formal statistical testing will be performed.

Summary statistics (mean, median, standard deviation [SD], range, proportion and 95% confidence intervals when appropriate) will be provided, by treatment groups for primary and secondary endpoints.

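### The per-protocol set requires an epoetin alfa dose in Weeks 18 to 20 of both arms, which a vadadustat subject on the assigned regimen should not have

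*Combined protocol and SAP*

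**What the plan says.** Section 11.2 defines the per-protocol population from all randomized subjects. Besides at least one dose of study drug and Hb values before and after treatment, they must "have epoetin alfa dose recorded during Week 18 to 20, and did not receive any rescue therapy from Weeks 12 to 20". The definition names no arm. The same section adds: "Efficacy analyses will utilize the MITT and per-protocol populations". Section 11.6 says that summary statistics "will be provided, by treatment groups for primary and secondary endpoints".

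Four other places govern epoetin in the vadadustat arm:

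- Section 8.3.5: "Subjects assigned to the vadadustat arm will discontinue epoetin alfa and take vadadustat once daily for 20 weeks".
- Section 8.4.2: "Subjects are prohibited from taking non-protocol ESAs starting from the screening period and through Week 20, unless the subject permanently discontinues study treatment". Rescue epoetin under 8.3.10 is allowed separately.
- Section 8.3.8: vadadustat subjects who complete Week 20, or stop early, "will resume dosing with epoetin alfa (or another ESA) at Week 20 after all EOT procedures are completed".
- Section 9.4.4 describes the same resumption as something subjects may do, where 8.3.8 says they will. Both allow epoetin alfa or another ESA.

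On missing data, section 11.5 expects few subjects to leave follow-up because of epoetin use, then says: "The primary analysis will be based upon observed data without imputation".

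**The concern.** A per-protocol set is meant to hold the subjects who took their assigned treatment as planned. Here one membership condition is a recorded dose of the comparator drug, and it applies to the arm that is told to stop that drug. A vadadustat subject who does what the protocol asks fails it, while one who abandons vadadustat and returns to epoetin may pass it.

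The set will be reported, because efficacy is analysed on both populations. The primary objective is the ability of vadadustat to raise Hb, so what is at stake is one of the two planned views of that effect. The study is descriptive with no formal testing, so the harm is a per-protocol mean and interval for vadadustat that do not describe subjects treated as planned. It is not an error-rate or power problem.

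**Working it through.** **1. Inputs.** 25 subjects per arm (11.1). The two per-protocol conditions are an epoetin dose recorded in Weeks 18 to 20 and no rescue in Weeks 12 to 20 (11.2). The plan states no expected size for the set, so there is no figure to reproduce; 25 × 2 = 50 agrees with the planned total.

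**2. The conditions applied to each kind of vadadustat subject.**

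| Vadadustat subject | Epoetin dose in Weeks 18 to 20 | Rescue clause | In the set? |
|---|---|---|---|
| Completes, no rescue, resumes epoetin at Week 20 | Only after the Week 20 procedures | Passes | Only if that dose counts |
| Completes, no rescue, resumes another ESA | None | Passes | No |
| Rescue epoetin in Weeks 18 to 20 | Yes | Fails | No |
| Stops vadadustat permanently, returns to epoetin | Yes, if still followed | Passes if no rescue in Weeks 12 to 20 | Possible |

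A recorded dose of zero would be a further route, but the text does not say that it counts.

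**3. Count.** Before the Week 20 assessments, the number of vadadustat subjects on regimen without rescue who have a qualifying dose is 0 of 25. In the epoetin arm, where epoetin is the assigned drug, it is up to 25 of 25.

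**4. The early-stop route.** Section 7.6.2.2 puts the end-of-treatment visit within 1 day of stopping study drug, if possible, followed by the 4-week follow-up. Footnote 8 of Appendix A gives the same sequence for leaving the study early. For a subject who stops at Week s, follow-up ends near s + 4. A dose recorded in Week 18 or later needs s + 4 ≥ 18, so s ≥ 14. Using the full ±5-day visit window gives 18 − 4 − 5/7 ≈ 13.3. On that schedule only those who stop from about Week 14 can qualify. If the final visit were instead held at calendar Week 24, earlier stoppers could qualify too.

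**5. Hb after rescue in the MITT summary, for scale.** The documents give no rescue rate, SD or duration of Hb lift, so any figure is assumed. A simulation took baseline Hb uniform on 8.5 to 10 g/dL, zero true effect, response SD 0.7 or 1.0, within-subject SD 0.5, and rescue from Week 6 at the 8.3.10 Hb limits. With 20 to 30% rescued, and rescue depending partly on factors outside the recorded Hb, the Week 20 bias in g/dL was:

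- all observed values, lift lasting 4 weeks: +0.02 to +0.04
- all observed values, lift lasting to Week 20: +0.12 to +0.27
- repeated-measures model setting aside Hb after rescue: +0.01 to +0.05

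At these rescue rates the model's standard error was 6 to 17% larger than that of the all-observed mean with the 4-week lift, and 18 to 41% larger with the lift to Week 20. If the missing-at-random assumption holds, the model's bias is about zero.

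**The case against.** The strongest reply is that the condition can be met. Section 8.3.8 places resumption at Week 20, and the window runs to Week 20, so completers who resume epoetin that day could qualify, with all their treatment-period Hb measured on vadadustat. This stands as a possible reading, and it rules out saying that the set must be empty. It does not rescue the rule: two subjects with identical vadadustat exposure would then be in or out according to the ESA chosen after the last efficacy measurement.

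A reader might infer more: that the set would hold a handful of subjects, all off vadadustat. The documents do not support this. They give no early-stopping rate. On the schedule in step 4 only late stoppers qualify, and their scheduled Hb up to the end-of-treatment visit was collected before or within about a day of stopping.

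A reader might also infer that the MITT summary is wrong because Hb after rescue enters the vadadustat mean. Section 11.5 does not support that. Its expectation that follow-up continues after epoetin use, followed by the observed-data rule, points to those values being kept. Rescue and transfusion proportions are already secondary endpoints. A model that sets aside Hb after rescue is a trade-off: its gain disappears if the lift is short or if missing at random fails, and its standard error is larger.

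**Conclusion.** The per-protocol definition is wrong as written for the vadadustat arm. Taken literally, no vadadustat subject who follows the regimen without rescue qualifies before the Week 20 assessments (0 of 25, against up to 25 of 25). The vadadustat set is then either near-empty, limited to late stoppers who returned to epoetin while still followed, or selected by which ESA was resumed. Which of these applies depends on whether a dose after the Week 20 procedures, or a zero dose, counts, and the text does not say. The resulting number of subjects cannot be computed from the documents.

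The condition may be left over from a design that kept epoetin in both arms, since section 9.3.3 still lists epoetin dose reduction for the vadadustat arm. That is inference. The conclusion rests on sections 11.2, 8.3.5, 8.3.8 and 8.4.2 alone.

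The handling of Hb after rescue in the MITT summary is not an error and needs no correction.

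**What to change.** In 11.2, replace the single dose condition with one for each arm: *for the epoetin alfa arm, an epoetin alfa dose recorded in Weeks 18 to 20; for the vadadustat arm, a vadadustat dose recorded in Weeks 18 to 20.* Removing the epoetin condition from the vadadustat arm without a replacement would let in subjects who stopped vadadustat early, so the second half matters. The Weeks 12 to 20 rescue clause can stay.

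The data are already collected: compliance questioning and accountability logs (8.3.7), review of dosing compliance at the Week 18 and Week 20 visits (9.4.3, 9.4.4), and the recorded time of the last dose at the Week 20 PK sample (8.3.7).

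The cost is one changed phrase. Subjects who stopped vadadustat before Week 18 leave the vadadustat per-protocol set. A subject whose vadadustat was interrupted under the protocol for the whole window would also leave it, so the text should say whether such an interruption counts as meeting the condition.

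A supplementary repeated-measures estimate that sets aside Hb after rescue is optional. If it is added, it should state its missing-at-random assumption and report the number of values set aside by arm and visit.
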